At the first outpatient follow-up visit, the VAS, STAI, and PONV scores will be repeated by study personnel. Patients will also fill out the device-specific survey at this time. Patients will also receive a phone call on device day 30 by the study coordinator, PI, or co-PI. At this time, the patient will again be asked to complete the VAS score, STAI, and PONV scores via telephone, and will be asked if he or she is still requiring narcotic pain medication, or if a refill of the narcotic pain medications was needed.

#### Device Removal

If the patient is discharged prior to the 5 day life of the BRIDGE device, he or she will be contacted via telephone by study personnel to obtain all remaining VAS, STAI, and PONV data on a daily basis until the evening of the fourth postoperative day (fifth device day). If the patient is hospitalized longer than the 5 day life of the BRIDGE device, the study coordinator, PI, or co-PI will remove the device according to standard

protocol. Prior to discharge, the patient will be instructed by a member of the study team on removal of the device after 5 days as well as what to do if the device is dislodged (see below). The subject will be given a handout with information on device handling and a place to record the date and time of device removal and date and time of device return. The handout will also contain contact information for study personnel. If a device falls off completely, it should not be reapplied. If individual electrodes are dislodged, they can be reapplied with household adhesive tape. If a patient requests withdrawal from the study or removal of the device before the 5-day life has expired, time of removal, VAS, STAI, and PONV scores will be recorded.

#### Follow-up phone call with study results

The device key will be opened 30 days after the final surgery per protocol. The patients will be contacted by phone to disclose the results of their device (active vs. inactive). Prior to disclosure of the device, the patients will be asked if they felt their device was active or inactive. This data will be recorded in order to determine if patient perception influenced results. Patients will also receive a letter disclosing the activity of their individual devices. Lastly, if results are significant and able to be published, patients will receive the publication by mail.

#### Data Collection

The following data will be extracted from the medical record:

- Surgical data:
  - Type of colon resection (right, left, sigmoid, total, etc.)
  - Operative technique (laparoscopic, hand-assisted, robotic, open)
  - Presence and type of ostomy, if applicable
- Demographics: age, sex, comorbidities, previous symptoms, diagnosis, indication for operation
- Total daily dosage of narcotics during hospitalization (milligrams of hydromorphone, converted to morphine equivalents), including intraoperative narcotics
- VAS scores (daily maximum and AUC)
- Number of emeses
- Laboratory values (if ordered by primary team)
- Respiratory depression, determined by need for opioid reversal agent (naloxone)
- Rescue methods for pain control (need for pain team consult, need for regional anesthesia)
- Complications (per Clavien-Dindo Classification)
- Return of bowel function (time to first flatus, time to first bowel movement)
  - Postoperative ileus, determined by need for NG tube insertion
- Length of stay (in days, including day of surgery)
- Rate of readmission
- Patient satisfaction scores
- Discharge destination (i.e. home, skilled nursing facility)
- Incidence of withdrawal (i.e. patients requesting to terminate study/remove device) and reason
- Need for additional narcotic prescription refills after discharge

The following data are study-specific and will be collected by the study personnel:

- STAI, and PONV scores during 5 day life of BRIDGE device, at a minimum once daily
- Need for device modification or removal, if applicable

- Biospecimens. Samples will be immediately de-identified after collection and coded with the study ID number. They will be stored in the Divisions research facilities de-identified for analysis.
- VAS, STAI, and PONV scores at first follow-up appointment as well as device day 30
- Device-specific survey

  

1. Bijur, P.E., W. Silver, and E.J. Gallagher, Reliability of the visual analog scale for measurement of acute pain. *Acad Emerg Med*, 2001. 8(12): p. 1153-7.
2. Scott, J. and E.C. Huskisson, Graphic representation of pain. *Pain*, 1976. 2(2): p. 175-84.
3. Julian, L.J., Measures of anxiety: State-Trait Anxiety Inventory (STAI), Beck Anxiety Inventory (BAI), and Hospital Anxiety and Depression Scale-Anxiety (HADS-A). *Arthritis Care Res (Hoboken)*, 2011. 63 Suppl 11: p. S467-72.

Title of Study: Auricular Percutaneous Electrical Nerve Field Stimulation for Postoperative Pain Control in Adults

NCT number: NCT02892513

Document Date: 10/4/2016

Auricular Percutaneous Electrical Nerve Field Stimulation for Postoperative Pain Control in Adults

Statistical analysis plan

Missing Data Handling

Every effort will be made to avoid missing data. Using logistic regression (LR), the assumption of missing at random data will be explored. If the data appear missing at random (MAR), multiple imputations for items and longitudinally random effects models will be used. If missing data appear not random, a sensitivity analysis will be employed, using clinical information and different assumptions to substitute values and see how results are affected.

Patient Demographics and Characteristics Data

Patient characteristics at baseline, demographic and disease characteristics will be summarized using descriptive statistics. In addition, previous and concomitant diseases and medications will be summarized. Frequencies will be presented for the categorical variables (e.g. race) and descriptive statistics will be presented for continuous variables (e.g. age).

Efficacy Variables

Aim 1 (Primary): To determine if auricular neurostimulation reduces visual analog pain scores and promotes decreased opioid usage, as measured by total hospital narcotic requirement in oral morphine equivalents.

Aim 2: To determine if auricular neurostimulation is associated with decreased postoperative nausea and vomiting, postoperative ileus, respiratory depression, and length of hospital stay.

Aim 3: To determine if auricular neurostimulation alters the biologic response to surgery.

Statistical Method

All efficacy data will be analyzed including modified intention to treat (mITT) patients. Per-protocol analysis will be done only if more than 10% of the ITT patients do not qualify for the per-protocol analysis. For all efficacy variables, the baseline value will be defined as the last value taken prior to the start of randomized study.

Continuous/Ordinal variables

Summary statistics such as mean, median, standard deviation, range and correlation plots and tree analysis will be used to examine distributions and interrelationships. Where necessary, for parametric assumption, we will employ appropriate transformations with justifications and compare using Student's t-test. If data cannot be appropriately transformed, we will compare variables between the two groups using a Mann-Whitney test. Pain scores will be analyzed using area under the curve for the entire hospitalization.

Categorical variables

We will compare the two groups using a chi - square or Fisher-Haltom exact test.

Power

For the efficacy outcomes, the main comparison of interest is total hospital narcotic requirement in oral morphine equivalents. For simplicity in power calculations, we use a (conservative) two sample two-sided t-test at an alpha of 0.05 on the change. For a power of 90%, assuming a 25% decrease in narcotic consumption with an average total hospital narcotic consumption of 180 mEq oral morphine log-transformed for normal distribution to 2.3 with standard deviation of 0.58, we would require 25 patients per group. Assuming a dropout rate of 10%, we estimate 28 participants in each group will be needed.

Safety Data

All safety variables (e.g., adverse events) will be summarized for each group (including follow-up) using descriptive statistics. Incidence of adverse events will be summarized by treatment.

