#### **Exclusion Criteria**

- History of chronic pain disorder (requiring continuous narcotic and/or NSAID use in the week prior to surgery), or active opiate abuse
- Need for emergent procedure, regional anesthesia (does not include escalation of medical management of pain), admission to ICU
- Prolonged postoperative intubation
- Use of intraoperative ketamine or lidocaine drips
- Refusal to receive follow-up phone calls
- Tape allergy/sensitivity
- Latex allergy
- Active pregnancy
- History of seizures
- History of cerebral aneurysm
- Recent organ transplant recipient
- Myocardial infarction within 6 months of study
- Anticoagulation (requiring fully therapeutic anticoagulant, not including anti-platelet agents such as aspirin or clopidogrel)
- Blood clotting disorder
- Other implantable devices/ on-demand electronic device
- MRI planned during study period
- Psoriasis, dermatitis, skin infections around ear

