### **Day of Surgery/First Day of Participation**

Upon presentation to the preoperative staging area on the day of surgery, subjects will first be asked by a member of the study team to rate their pain (VAS scale), anxiety (STAI scale), and nausea (PONV scale). The Visual Analog Scale (VAS) is a nearly universal score which rates patients' pain on a scale of 0-10. This scale has been well studied and has been employed by both participating institutions as the primary grading system for pain.(1,2) Anxiety will be measured with the State-Trait Anxiety Inventory (STAI), originally published in 1970 as a method to evaluate current anxiety (state anxiety) as well as propensity to become anxious (trait anxiety).(3) The postoperative nausea vomiting (PONV) scale has been shown to be a reliable measure of nausea, and has also been used at both participating institutions.(4) The patients will also submit a blood sample and buccal swab prior to surgery. As standard of care, a urine pregnancy test is a routine preoperative lab for all females of childbearing age. As such, this test will be performed on the morning of surgery.

*Auricular Neurostimulation Details and Application:*

This protocol has been generously shared by our colleagues at CHW, based on an ongoing, IRB-approved trial (CHW14/208; clinicaltrials.gov # NCT02367729). It has been adapted to fit our patient population. The BRIDGE is an FDA-approved (510(k)140530) and commercially available device manufactured by Key Electronics (Jeffersonville, IN, USA) and distributed by Innovative Health Solutions (Versailles, IN, USA). BRIDGE is an ambulatory, neurological device which consists of a battery powered, externally affixed generator with 4 wire leads attached to 3 electrode/needle arrays and one single point needle. The arrays are designed to produce a field effect similar to surgically implanted peripheral neurostimulators. One BRIDGE device per patient will be used in this study.

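### The powered opioid comparison is unadjusted although age and a pre-placement STAI are collected; prespecifying both as covariates is a cheap efficiency gain if they predict opioid use

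*SAP*

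**What the plan says.** The SAP's Power section states that "the main comparison of interest is total hospital narcotic requirement in oral morphine equivalents". For continuous outcomes, the section on continuous and ordinal variables says "we will employ appropriate transformations with justifications and compare using Student's t-test"; failing a suitable transformation, "we will compare variables between the two groups using a Mann-Whitney test". Neither sentence names a covariate, and no regression model for the opioid total appears elsewhere in the SAP. Random effects models are mentioned only under Missing Data Handling. Correlation plots and tree analysis are listed as ways to examine distributions and interrelationships. The SAP defines a baseline value for every efficacy variable, but in-hospital opioid use has no baseline value for that definition to pick up.

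Two candidate covariates are already collected:

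- **Anxiety.** On arrival on the day of surgery, patients "rate their pain (VAS scale), anxiety (STAI scale), and nausea (PONV scale"). The protocol places the device only after these questionnaires. The full STAI is scheduled for device day 1. The Device Removal section equates the fourth postoperative day with the fifth device day, so device day 1 is the day of surgery.
- **Age.** The protocol's Data Collection list includes "Demographics: age, sex, comorbidities, previous symptoms, diagnosis, indication for operation".

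Randomisation is 1:1 in blocks of 10, with no stratification factor named.

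**The concern.** Neither the design nor the analysis uses any baseline information on the outcome that sets the sample size. The trial is small (25 evaluable per arm planned, 28 randomised) and the stated SD of 0.58 on the log scale is large. The protocol itself recognises that chance imbalance can matter in a study of this size: it gives that as one reason for prohibiting NSAIDs.

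If age and preoperative anxiety predict opioid demand, part of the residual variance could be removed at almost no cost, giving a narrower interval for the main effect. If the covariates are not fixed in advance, any later adjusted result could be suspected of having been chosen after looking at the data, the more so because exploratory tree analysis is planned.

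**Working it through.** **Inputs from the SAP, Power section.** SD 0.58 on the log scale; 25 per group, 28 after 10% dropout; two-sided alpha 0.05; power 90%; mean 180 mEq, logged to 2.3. Since log10(180) = 2.26, the scale appears to be log10.

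**Assumed.** Joint R-squared of age and one STAI score with log opioid use. The documents give no value, so 0 to 0.30 is shown.

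**The plan's own figure.** The stated 25 is approached only if the 25% decrease is applied to the log mean: 0.25 × 2.3 = 0.575, and 0.575/0.58 = 0.991 SD. The two-sample t-test then needs 23 per group for 90% power, or 23/0.955 = 24.1, rounded up to 25, with the usual Mann-Whitney efficiency. Dropout: 25/0.90 = 27.8, rounded up to 28. With 25 per group and this difference, unadjusted power is 93.0%.

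**Unadjusted interval.** Half-width = t(0.975, 48) × 0.58 × √(2/25) = 2.011 × 0.58 × 0.2828 = 0.330.

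**Adjusted interval, k = 2 covariates.** Residual df = 50 − 2 − 2 = 46. The variance inflation for chance covariate imbalance is (2n − 3)/(2n − 3 − k) = 47/45 = 1.044. Half-width = t(0.975, 46) × 0.58 × √(1 − R²) × √(2/25 × 47/45), with t(0.975, 46) = 2.013.

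| Joint R² (assumed) | Half-width (log scale) | Ratio to unadjusted | Power for a difference of 0.575 |
|---|---|---|---|
| Unadjusted | 0.330 | 1.000 | 93.0% |
| 0 | 0.337 | 1.023 | 91.9% |
| 0.10 | 0.320 | 0.971 | 94.3% |
| 0.20 | 0.302 | 0.915 | 96.4% |
| 0.30 | 0.282 | 0.856 | 98.0% |

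**Break-even.** The squared ratio at R² = 0 is (47/45) × (2.0129/2.0106)² = 1.0468, so adjustment pays once R² exceeds 1 − 1/1.0468 = 0.045.

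**Limit of what this can do.** A true 25% decrease is log10(0.75) = −0.125 on the log10 scale. The half-width is more than twice that whether unadjusted (0.330) or adjusted at R² = 0.30 (0.282). Power for that difference at 25 per group is 11.6% unadjusted and 14.1% with two covariates at R² = 0.30.

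**The case against.** The strongest reply is that nothing is wrong: randomisation makes the unadjusted test valid, its standard error already reflects chance imbalance, and no document shows that age or anxiety predicts opioid use. This stands. A reader might infer that precision is certainly being lost, or that the planned estimate is biased. The documents support neither: the gain is conditional on an unknown R-squared, and below about 0.045 adjustment slightly widens the interval. The Screening and Informed Consent section also excludes patients with an anxiety disorder on anxiolytics, which may narrow the STAI range and weaken that covariate.

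A reader might also want preoperative opioid use as a third covariate, since screening mentions it. The documents do not support that. The criterion concerns a chronic pain disorder "requiring continuous narcotic and/or NSAID use in the week prior to surgery", together with active opiate abuse. It does not record whether a patient took any opioid that week, and it removes the continuous users. A yes/no item would be a new and possibly sparse variable. The SAP does plan to summarise previous medications, but defines no such item.

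A further reply is that adjustment changes little in practice. On the plan's own difference of 0.575, power is already 93.0%; on a true 25% reduction, it stays very low either way. This too is fair, and it is why the point should not be presented as a remedy for the sample size.

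What survives is narrower: two covariates are already in hand, the possible loss is small and bounded, and naming them in advance protects the credibility of any adjusted result.

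**Conclusion.** The point holds as an efficiency recommendation. The main opioid comparison uses no baseline information although age and a pre-placement STAI are available. With 25 per arm, two covariates and an assumed joint R-squared of 0.10, 0.20 or 0.30, the 95% interval would be about 3%, 8% or 14% narrower. The worst case, with no prognostic value at all, is about 2.3% wider. These ratios do not depend on the SD or on the base of the logarithm, but they do assume a linear relation on the log scale and 25 evaluable patients in each arm.

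It would be wrong to conclude that adjustment rescues the trial's power. The mismatch between a 25% reduction and the difference that reproduces the stated sample size is a separate and larger problem.

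**What to change.** State in the SAP, before the device key is opened, that log-transformed total hospital opioid use will be analysed by a linear model with arm, age and one pre-placement STAI subscale score. Report the ratio of geometric means with its 95% confidence interval, and keep the unadjusted t-test or Mann-Whitney test as supportive. Say explicitly that the Mann-Whitney test remains the fallback if no transformation is adequate.

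Name the STAI subscale. The protocol needs reconciling here: the Day of Surgery section treats state anxiety as current and trait anxiety as a propensity, while the Intraoperative and Postoperative Protocol labels the first page as trait anxiety and calls it transient.

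Do not add preoperative opioid use as a covariate.

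The cost is SAP wording and two degrees of freedom, with no new visit, procedure or data item. The statisticians are blinded and the key is opened only 30 days after the final surgery, so the choice can be fixed credibly before then.

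### The stated 25 patients per group give about 12% power, not 90%, for a 25% fall in opioid use; the 25% appears to have been taken off the logged mean.

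*SAP*

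**What the plan says.** The SAP's Power section is the only sample-size justification in either document. It states that "the main comparison of interest is total hospital narcotic requirement in oral morphine equivalents", and the protocol's Intraoperative and Postoperative Protocol likewise names opioid use as the primary outcome.

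The calculation is described as a "two sample two-sided t-test at an alpha of 0.05 on the change". The target is given as follows: "For a power of 90%, assuming a 25% decrease in narcotic consumption". The control level is an "average total hospital narcotic consumption of 180 mEq oral morphine", and the sentence goes on to the log-scale inputs and the result: "log-transformed for normal distribution to 2.3 with standard deviation of 0.58, we would require 25 patients per group". That number is raised to 28 per group for 10% dropout.

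The section states neither the base of the logarithm nor the difference on the log scale that was entered into the calculation.

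**The concern.** A percentage reduction in a quantity becomes a fixed subtraction on the log scale, whatever the starting level. A 25% decrease on log10 is a shift of 0.125. Against an SD of 0.58 that is a small standardised effect, and small effects are not detected with 90% power by 25 patients per group. The stated number fits a standardised effect near 1, which is what results if 25% is removed from the logged mean instead of from the consumption.

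The primary comparison would then lack the power claimed for it. If the trial gave a non-significant result, anyone reading it beside the SAP would take a 25% opioid reduction to have been largely excluded, when the trial had little chance of showing one.

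A lesser point in the same sentence is that the test is said to be on a change. Total hospital opioid requirement accumulates after randomisation and has no baseline value to subtract.

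**Working it through.** **Inputs (SAP, Power, unless noted).** Control average 180; log mean 2.3; log SD 0.58; 25% decrease; two-sided alpha 0.05; power 90%; 10% dropout. Allocation is 1:1 (protocol, randomisation section).

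**Scale.** log10(180) = 2.255, which rounds to 2.3; ln(180) = 5.19. The log mean is on log10.

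**Formulas.** Standardised effect d = δ/SD. Normal approximation: n per group = 2(1.960 + 1.282)²/d² = 21.0/d². The exact figures below use the noncentral t distribution.

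**Reproducing the plan's figure.** Take 25% off the log mean:
- With the rounded mean, δ = 0.25 × 2.3 = 0.575 and d = 0.575/0.58 = 0.991. Then n = 22.4, so 23 per group; power at 25 is 93%.
- With the unrounded mean, δ = 0.25 × 2.255 = 0.564 and d = 0.972. Then n = 23.2, so 24 per group; power at 25 is 92%. Dividing 23.2 by 0.955, a usual allowance for a rank test, gives 24.3, so 25.
- Dropout: 25/0.90 = 27.8, so 28, as stated.

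A shift of 0.575 on log10 is a ratio of 10^(−0.575) = 0.266. That is a 73% fall, from 180 to about 48.

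**Applying the 25% to consumption.**
- δ = |log10(0.75)| = 0.125; d = 0.1249/0.58 = 0.215.
- Power at 25 per group: d√(n/2) = 0.2154 × √12.5 = 0.762, and Φ(0.762 − 1.960) = 11.5%. The noncentral t gives 11.6%. At 28 per group it gives 12.4%. Simulation gave 11.5% and 12.4%.
- n for 90% power: 453.8, so 454 per group, or 454/0.90 = 505 per group with dropout.

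**What 25 per group can detect.**
- 90% power: d = 0.936, δ = 0.936 × 0.58 = 0.543, ratio 10^(−0.543) = 0.287. That is a 71% lower geometric mean (180 to about 52).
- 80% power: about a 66% reduction.
- Expected 95% confidence interval half-width: 2.01 × 0.58 × √(2/25) = 0.330 on log10, a factor of 10^0.330 = 2.1 each way on the ratio.

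**Other readings of the inputs.**

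| Reading | δ | d | Power at 25 | n per group for 90% |
|---|---|---|---|---|
| 25% off consumption, log10 SD 0.58 | 0.125 | 0.215 | 11.6% | 454 |
| 2.3 taken as exact, against log10(135) | 0.170 | 0.293 | 17% | 247 |
| 0.25 taken directly as the log10 difference | 0.25 | 0.431 | 32% | 115 |
| 0.58 taken as a natural-log SD, δ = \|ln 0.75\| | 0.288 | 0.496 | 40% | 87 |

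Relaxing the test does not help. In the first row, a one-sided test at 90% power needs 370 per group, and a two-sided test at 80% power needs 340. For 25 per group to give 90% power for a 25% decrease, the log10 SD would have to be 0.1249/0.936 = 0.134, less than a quarter of the stated 0.58.

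**The case against.** The strongest reply is that the SAP does not show the difference it used, so the slip is inferred. Removing 25% of the log mean gives 23 or 24, not 25. Reaching 25 takes a rank-test allowance that the Power section does not mention; there the test is a t-test. This stands as a limit on the explanation: the plan can be said to look as if it did this, not to have certainly done it. It does not rescue the power claim, since none of the readings tried gives more than 40%.

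A second reply is that 12% depends on 0.58 being a log10 SD, and the SD may itself be wrong. A log10 SD of 0.58 in a lognormal distribution implies a coefficient of variation of about 220%. It also puts the arithmetic mean at 2.44 times the geometric mean, so 180 as a geometric mean would go with an arithmetic mean near 439. If 180 is an arithmetic average, the three inputs do not fit one lognormal distribution. This is a good reason to check the SD before fixing any replacement figure. It does not alter the power for a proportional reduction, which depends only on the ratio and the log SD. The falls from 180 to 48 and to 52 do treat 180 as a geometric mean.

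Third, the reference to change may be loose wording for the difference between groups, and the protocol itself calls the study small. Both are fair. The wording point is minor and plays no part in the arithmetic. Acknowledging a small study does not make the 90% figure correct.

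**Conclusion.** The concern holds. On the SAP's own inputs, 25 per group give about 12% power for a 25% decrease in opioid consumption, not 90%. The trial would miss a true 25% reduction almost nine times in ten. The stated power belongs to a fall of roughly 71% to 73%.

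This rests on four assumptions: 0.58 is the SD on log10, as the adjacent 2.3 implies; the 25% is a proportional reduction in consumption; both groups share the log-scale SD; and the comparison is unadjusted, as the SAP plans. Relaxing the first, against the evidence of the 2.3, raises power to about 40%. That the 25% was applied to the logged mean is the likely explanation, but the verdict does not depend on it.

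**What to change.** First confirm the log base and the source of the 0.58. If it is not a log10 SD, correct it and recompute before restating anything.

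If it is confirmed, keep 25 to 28 per group and replace the power statement with text such as:

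> With 25 evaluable patients per group and a log10 SD of 0.58, a two-sided two-sample t-test at alpha 0.05 has 90% power to detect a log10 difference of 0.54, that is, about a 71% lower geometric-mean consumption. Power for a 25% decrease is about 12%.

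Remove the reference to change from the description of the test. State that the trial is a pilot with respect to effects of about 25%, and report the ratio of geometric means with its 95% confidence interval, so that a non-significant result is read by the effects it leaves open.

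This changes SAP wording only and adds no patients. The real cost is that the stated justification becomes less favourable. If the sponsor wants to keep 90% power for a 25% decrease, about 454 evaluable patients per group would be needed at this SD.
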